8.5 EXAMINATION OF SUBGROUPS

Statistical tests for interaction (between subgroup and treatment arm) will be performed to decide about the need to further investigate subgroups of the trial population based on the following variables:

- age group (< median vs \geq median, where median is calculated based on ENR population)
- gender (Male vs Female)
- Status (Male, Female pre-menopausal status, Female post-menopausal status);

Subgroup analysis will be performed if interaction effects are statistically significant at 0.15 level of significance.

Subgroup analysis will be performed for the primary efficacy endpoints. Descriptive and appropriate inferential statistical tests will be used. All subgroups will be analysed using FAS population.

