9.5.6. Specification of subgroups for analysis

Statistical tests for interaction (between subgroup and treatment arm) will be performed to decide about the need to further investigate subgroups of the trial population based on the following variables: age group, gender and Country.

Subgroup analysis will be performed if interaction tests are statistically significant at 15% nominal level. Statistical details and potential new subgroups definitions will be reported in the SAP.

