18 CHANGES FROM PROTOCOL

Following are the changes from the protocol:

- a. Specification of additional populations-All Patient Enrolled (ENR) and Randomized Population (RND).
- b. Text “Subjects”, “Participants” changed to “Patients”.
- c. Baseline characteristics “gender” and “Child-bearing potential status” are combined and derived a new categorical variable with categories Male, Female pre-menopausal status and Female post-menopausal status to be included as factor “Status” in the statistical model of analysis of efficacy endpoints.
- d. Due to the premature interruption of the enrolment, no interim analysis will be done.

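### Subgroup results appear only if an interaction test reaches p<0.15; at 68 patients this favours large estimates and leaves consistent ones unreported

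*SAP*

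**What the plan says.** SAP 8.5 tests treatment-by-subgroup interactions for age group (split at the median), gender and a three-level variable, "Status (Male, Female pre-menopausal status, Female post-menopausal status". It then states: "Subgroup analysis will be performed if interaction effects are statistically significant at 0.15 level of significance". The subgroup analysis covers the two primary efficacy endpoints in the full analysis set.

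The condition comes from the protocol. Section 9.5.6 reads: "Subgroup analysis will be performed if interaction tests are statistically significant at 15% nominal level". Its variable list differs, being "based on the following variables: age group, gender and Country". It also leaves room for the SAP to extend that list: "Statistical details and potential new subgroups definitions will be reported in the SAP".

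SAP section 18 opens with "Following are the changes from the protocol" and gives four items. Item (c) introduces Status as a factor "in the statistical model of analysis of efficacy endpoints". No item mentions that the Country subgroup is gone, or that Status is now a subgroup variable.

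SAP 4.3 records that enrolment stopped at 68 patients. SAP 14.1.1 describes primary models that include interactions of treatment with center, age and status, plus baseline NEWS for the clinical endpoint. Table 3 of the SAP does not list those interactions.

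**The concern.** Subgroup tables are usually read to see whether the treatment effect is similar across patient types. Under this condition, a similar effect is the one result for which no subgroup estimate is planned. The estimates that do appear have been selected because the observed difference was large, so on average they overstate the true difference.

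This matters most for sex and menopausal status. Protocol section 2.6 builds the case for raloxifene partly on sex hormones and oestrogen-receptor modulation, and 2.6.2 expects benefit in both men and women. A reader of the report will want those estimates, however imprecise. When the SAP was written it was known that the trial had ended at 68 patients, so the condition could have been reconsidered then.

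**Working it through.** The plan derives no figure from the 0.15 level, so there is none to reproduce. On one degree of freedom, two-sided p<0.15 means |z| > 1.4395.

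**Inputs.** 68 patients (SAP 4.3); 1:1:1 allocation, and planned rates of 25% to 50% (virologic) and 50% to 75% (clinical) (SAP 4.1.2). Both pairs of rates give an odds ratio of 3. Assumption: the subgroup variable splits the sample in half. The documents give no sex or age split, and a half split cannot describe three-level Status.

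**1. Patients per arm and subgroup.** 68 / (3 × 2) = 11.33.

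**2. Interaction needed to pass, one dose versus placebo.**
- Variance of the log ratio of odds ratios = 2 × [1/(11.33 × 0.25 × 0.75) + 1/(11.33 × 0.50 × 0.50)] = 2 × (0.4706 + 0.3529) = 1.647.
- SE = 1.283.
- Observed ratio needed: exp(1.4395 × 1.283) = 6.3 or more, or 1/6.34 = 0.16 or less.
- The clinical rates involve the same two variance terms and give the same result.

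**3. Chance of passing when a real interaction exists.** Suppose the true ratio of odds ratios is 3, meaning the planned effect in one half and none in the other. Then ln 3 / 1.283 = 0.856, and the probability is Φ(0.856 − 1.4395) + Φ(−0.856 − 1.4395) = 0.280 + 0.011 = 0.29. When it passes in the right direction, the observed ratio is at least 6.34 / 3 = 2.1 times the truth.

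On the difference scale, for a true 25-point interaction:
- Virologic: SE = √[(3 × 0.1875 + 0.25)/11.33] = 0.268. The smallest passing difference is 1.4395 × 0.268 = 0.385, about 38 points; power is 32%.
- Clinical: SE = √[(3 × 0.25 + 0.1875)/11.33] = 0.288. The smallest passing difference is 0.414, about 41 points; power is 30%.

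At 108 per arm ((150 + 174)/3, the expected full size), the smallest passing differences are 18 to 19 points and power is 68 to 73%.

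**4. Chance of passing when no interaction exists.** Three variables on two endpoints give six tests, if each variable has one test across all arms. If independent, 1 − 0.85⁶ = 0.62, with 6 × 0.15 = 0.9 passes expected. Testing each dose separately gives 12 tests and 1 − 0.85¹² = 0.86. The SAP does not say which is meant.

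Gender is nested in Status, so the tests are not independent. A simulation of 3,000 trials of 68 patients used likelihood-ratio tests and assumed half female, a quarter of females pre-menopausal, no other covariates and no missing data. Each test passed 18 to 25% of the time, and at least one passed in 69% of trials. At 324 patients the figure was 58%. The individual rates exceed 15% because the cells are small. SAP 14.1.1 specifies Wald p-values for the primary model, while 8.5 names no test. Wald tests reject less often in sparse cells, so the figure would then be lower and more subgroup results would go unreported.

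**5. What unconditional reporting would show.** For one dose versus placebo within a half-sample subgroup, SE = √[(0.1875 + 0.25)/11.33] = 0.1965. The 95% interval is ±1.96 × 0.1965 = ±0.385, about ±38 points. For the difference between two subgroups it is ±0.385 × √2 = ±0.545, about ±54 points.

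**The case against.** Most of the case on the other side is sound, and it limits the point.

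- **The condition is pre-specified in the protocol.** The SAP carries it over unchanged, so it is not an SAP deviation. This stands: the criticism applies to both documents, and removing the condition must itself be declared as a change.
- **The sample size causes the imprecision.** The 0.15 level is lenient, and the large passing threshold follows from stopping at 68. This stands. Unconditional reporting removes the selection but does not supply the missing information.
- **Interactions are examined anyway.** The tests in 8.5 are run whatever the result, and 14.1.1 puts treatment interactions in the primary models. This stands in part. The output planned there is an odds ratio for each active arm against placebo, not an estimate within each subgroup, and covariates may be removed if the model does not converge.
- **No conclusion depends on it.** Superiority rests on the four primary null hypotheses alone. This stands and keeps the point minor.

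A reader might infer that the differences reported would be mostly chance. The documents cannot show that. The 62% is the probability of at least one pass when no interaction exists; it is not the share of passes that are false. With 30% power, that share is 0.15(1 − π) / [0.15(1 − π) + 0.30π], where π is the proportion of true interactions. It is 33% for π = 50% and 90% for π = 5%, and the documents give no basis for choosing π. Nor is every reported effect exaggerated; selection inflates on average.

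A reader might also link the loss of Country to selective reporting. The two are separate. Protocol 9.5.6 allows new subgroup definitions, so adding Status is permitted, and center remains in the model. Three countries were planned, but patient numbers per country are not given, so a Country analysis may not be estimable. What remains is an undeclared omission.

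**Conclusion.** The point holds as a minor one. At 68 patients, the condition shared by protocol 9.5.6 and SAP 8.5 releases subgroup estimates selected for being large and withholds consistent ones. Its size is a passing threshold of about 6.3 on the ratio of odds ratios, roughly a 29 to 32% chance of detecting a true ratio of 3 or a 25-point interaction, and roughly a 60 to 70% chance of at least one pass when nothing is there.

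The first two figures assume a half split, the planned rates and a single-dose contrast. The last assumes six tests that hold their nominal level or are likelihood-ratio tests. The direction of the problem does not depend on these assumptions; the sizes do. Without the condition, the trial still could not establish consistency across sex or menopausal status, but the report would no longer show a selected set of estimates.

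The absence of Country from SAP 8.5, undeclared in section 18, is a separate documentation gap.

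**What to change.** In SAP 8.5, report each active arm against placebo, with a 95% interval, for every pre-specified subgroup and both primary endpoints, whatever the interaction p-value. Give that p-value as description only, and state whether it is one test across arms or one per dose. List the change in section 18 as a departure from protocol 9.5.6.

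Separately, state in section 18 that the Country subgroup was dropped and why, or restore it if numbers per country allow.

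The cost is a few extra tables or one forest plot per endpoint. The intervals will be very wide, so a sentence should warn that they neither show nor exclude consistency.

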9 OUTPUT PRESENTATIONS

SAP Section 17 and Appendix 1 includes conventions for presentation of data in outputs.

The templates provided with this SAP describe the presentations shell for this study and therefore the format and content of the summary tables, figures and listings to be provided.

The reference analysis population of each table and line listing will be reported in the corresponding table, listing and figures.

10 PATIENT DISPOSITION, WITHDRAWALS AND PROTOCOL DEVIATIONS

A detailed description of the patient disposition will be provided. The number of patients screened, screen failures, randomized, randomized but not dosed, completed, as well as the number of dropouts, with reasons for treatment discontinuation, study discontinuation and major protocol deviations. The summary of analysis populations, a summary of reasons for exclusion from analysis populations will be presented.

Patient disposition details will be presented in listing.

Furthermore, Summary of Protocol Deviations table and an individual data listing of protocol deviations will be produced.

The Enrolled (ENR) population will be considered for this analysis. And data will be summarized by randomized treatment group.

11 DEMOGRAPHIC AND OTHER BASELINE CHARACTERISTICS

Summary of demographic data and other baseline characteristics will be tabulated for the Full analysis set (FAS) population and will be summarized by randomized treatment group.

No statistical testing will be carried out for demographic or other baseline characteristics.

The following demographic and baseline characteristics will be reported by treatment for this study:

- Demographic variables:
 - Age (years)
 - Sex (Male, Female)
 - Race (White, Black or African American, Asian, American Indian or Alaska native, Native Hawaiian or other pacific islander, NA, Other)
 - Height (cm)
 - Weight (Kg)

- BMI
- Smoking habits
- Status (Male, Female pre-menopausal status and Female post-menopausal status)
- Female Patient childbearing potential (Yes/No)

Default frequency tabulations will be provided for categorical variables and descriptive statistics will be provided for quantitative parameters.

11.1 MEDICAL HISTORY

Medical history information will be tabulated for both FAS and SAF analysis populations and will be summarized accordingly (see SAP section 5).

All verbatim terms will be assigned to a Preferred Term (PT) and will be classified by primary System Organ Class (SOC) according to MedDRA dictionary September 2020, version 23.1

Medical conditions which are not ongoing at Screening visit will be considered as previous diseases while those reported as "ongoing" in CRF will be considered as concomitant diseases.

Medical History of special interest as per collected in CRF will be listed for ENR population.

12 PRIOR AND CONCOMITANT MEDICATIONS

All medications taken by the patients during the Screening will be recorded by the Investigator in the CRF.

Prior and concomitant medications will be tabulated for both the FAS and SAF analysis populations and will be summarized accordingly. Prior and concomitant medications will be coded using WHODD Global September2020 version.

See Appendix 2 for handling of partial dates for medications, in the case where it is not possible to define a medication as prior or concomitant, the medication will be classified by the worst case, i.e., concomitant.

Prior medications are those which stopped prior to the date of first study medication administration.

Concomitant medications are those which

- started prior to, on or after the date of first study medication administration and started no later than end date of the study, and
- ended on or after the date of first study medication administration or were ongoing at the end of the study.

The following tables will be presented:

- A frequency tables of prior medications by primary therapeutic subgroup (ATC level subgroup) and generic name.
- A frequency tables of concomitant medications by primary therapeutic subgroup (ATC level subgroup) and generic name.

Listing of prior/concomitant medication will be provided.

13 STUDY MEDICATION EXPOSURE AND COMPLIANCE

13.1 DURATION OF EXPOSURE AND TREATMENT COMPLIANCE

Data will be summarized by actual treatment groups for Safety (SAF) population with descriptive statistics.

Total duration of study medication exposure considered in days and will be summarized using descriptive statistics.

Study medication taken (# of capsules) will be summarized using descriptive statistics.

Descriptive statistics will be presented separately by treatment group for the overall compliance to study medication. The overall compliance categories

- $\leq 80\%$,
- $>80 - \leq 100\%$, and
- $>100\%$

will be summarized using frequency and percent by treatment.

Additionally, the individual table will be provided for

- study medication taken (capsules) and overall compliance on Day 1 i.e., two oral doses in the first day of treatment.
- study medication taken (capsules) and overall compliance after Day 1 i.e., a single daily oral dose of patients for two weeks.

All the patient's data will be listed.

The following derivation rules will be applied:

Total duration of exposure (days) = (Treatment end date – Treatment start date) + 1.

- Overall Compliance (%) = (number of capsules taken / expected number of capsules to be taken during the study (i.e., 30)) *100
- Overall Compliance on Day 1 (%) = (number of capsules taken in first day / expected number of capsules taken in first day intake (i.e., 4)) *100
- Overall Compliance after Day 1 (%) = (number of capsules taken after the first day / expected number of capsules to be taken after the first day (i.e., 26)) *100

14 ANALYSES OF EFFICACY VARIABLES

14.1 EFFICACY ANALYSES

NEWS score evaluation will be performed at T0, T7, T14 and T28. NEWS score and NEWS score parameters as per collected in CRF will be provided in Listing for FAS population. Refer Appendix 3 for NEWS score.

Table 3: Summary of Analyses Strategies for efficacy endpoints:

Endpoint	Analysis set	Statistical method	Factors/Co variates	Missing data Handling	Analyses type
Virologic outcome - Proportion of patients with undetectable SARS-CoV-2 at PCR at day 7 after randomization.	FAS	Binary Logistic regression	Treatment, center, age and status	Missing data will not be imputed	Primary analysis
Virologic outcome - Proportion of patients with undetectable SARS-CoV-2 at PCR at day 7 after randomization.	PP	Binary Logistic regression	Treatment, center, age and status	Missing data will not be imputed	Sensitivity analysis
Clinical outcome - Proportion of patients who does not require supplemental oxygen therapy (NEWS ≤2) and/or mechanical ventilation at day 14 after randomization.	FAS	Binary Logistic regression	Treatment, center, age, status and baseline NEWS	Missing data will not be imputed	Primary analysis
Clinical outcome - Proportion of patients who does not require supplemental oxygen therapy (NEWS ≤2) and/or mechanical ventilation at day 14 after randomization.	PP	Binary Logistic regression	Treatment, center, age, status and baseline NEWS	Missing data will not be imputed	Sensitivity analysis

14.1.1 PRIMARY EFFICACY ENDPOINTS AND ANALYSES

1. Proportion of patients with undetectable SARS-CoV-2 at PCR at day 7 after randomization (virologic endpoint). This endpoint will be derived as below.
 - Based on Approved molecular test (PCR) result at day 7, the responses will be considered as “detectable” if PCR result is “Positive” otherwise “undetectable” if PCR result is “Negative” (Missing PCR result will be considered as missing in the main analysis).

The response (detectable / undetectable) at day 7 will be analysed using Binary logistic regression model with treatment group and pre-defined baseline factors (center, age, status and their interaction effects with treatment group). Odds ratio

will be computed for comparisons of each active treatment group versus placebo. i.e., raloxifene (60 mg) versus placebo and raloxifene (120 mg) versus placebo.

2. The proportion of patients who does not require supplemental oxygen therapy (NEWS ≤ 2) and mechanical ventilation at day 14 after randomization (clinical endpoint). This endpoint will be derived as below.

- If collected NEWS score > 2 or mechanical ventilation at day 14 result “Yes” then the response will be considered as “Required”. If collected NEWS score ≤ 2 and mechanical ventilation with result “No” then the response will be considered as “Not Required” (if both NEWS score and mechanical ventilation are missing, patient will be considered as missing).

The response (Required/ Not required) at day 14 will be analysed using Binary logistic regression model with treatment group and pre-defined baseline factors (center, age, status, baseline NEWS and their interaction effects with treatment group). Odds ratio will be computed for comparisons of each active treatment group versus placebo. i.e., raloxifene (60 mg) versus placebo; and raloxifene (120 mg) versus placebo.

For both virologic and clinical endpoint, Binary Logistic regression will be performed using PROC GENMOD in SAS® on the observed data only to estimate difference in proportions between each active treatment versus placebo and its corresponding 95% (2-sided) confidence intervals. Exponential transformation will be used to obtain the odds ratio and corresponding 95% confidence interval. P-values will be reported based on the Wald tests from Type III analyses. Bonferroni method will be considered to handle multiple treatment comparisons.

In the SAS® procedure PROC GENMOD, a Type III analysis will be performed by adding the model options: TYPE3, DIST=BIN and LINK=LOGIT.

If the model does not converge then the following steps will be performed subsequently:

- PROC GENMOD with EXACT statement will be used.
- If the model still does not converge, then remove the factors/covariates from the model one by one (according to statistical significance) until convergence reached.
- If the model still does not converge, then perform the Fisher's exact using the SAS procedure PROC FREQ without adjusting for any pre-defined factor and covariates.

The following hypotheses will be tested:

- The null hypothesis for the virologic endpoint is that proportion of treated patients with undetectable SARS-CoV-2 at PCR at day 7 after randomization ($\pi_{RALOXIFENE}$) is lower or equal the placebo one ($\pi_{PLACEBO}$). Two sets of null and alternative hypotheses are provided, one for each treatment dosage:

$$H_{01-60mg}: \pi_{RALOXIFENE-60mg} \leq \pi_{PLACEBO}$$

$$H_{11-60mg}: \pi_{RALOXIFENE-60mg} > \pi_{PLACEBO}$$

$$H_{01-120mg}: \pi_{RALOXIFENE-120mg} \leq \pi_{PLACEBO}$$

$$H_{11-120mg}: \pi_{RALOXIFENE-120mg} > \pi_{PLACEBO}$$

- The null hypothesis for the clinical endpoint is that proportion of treated patients who does not require supplemental oxygen therapy (NEWS ≤ 2) and/or mechanical ventilation at day 14 after randomization ($T_{RALOXIFENE}$) is lower or equal the placebo one ($T_{PLACEBO}$). Two sets of null and alternative hypotheses are provided, one for each treatment dosage:

$$H_{02-60mg}: T_{RALOXIFENE-60mg} \leq T_{PLACEBO}$$

$$H_{12-60mg}: T_{RALOXIFENE-60mg} > T_{PLACEBO}$$

$$H_{02-120mg}: T_{RALOXIFENE-120mg} \leq T_{PLACEBO}$$

$$H_{12-120mg}: T_{RALOXIFENE-120mg} > T_{PLACEBO}$$

Superiority of raloxifene will be established if at least one null hypothesis is rejected.

The frequency and percent will be presented by treatment and visit for both primary endpoints results.

The following figures will be produced for both primary endpoints results:

- Bar chart for Proportion of Patients with undetectable SARS-CoV-2 at PCR by treatment and visit
- Bar chart for Proportion of Patients who does not require supplemental oxygen therapy (NEWS ≤ 2) and/or mechanical ventilation by treatment and visit

The following listings will be presented:

- Listing for the Nasopharyngeal Swab Test (PCR) results
- Listing for the supplemental oxygen therapy (NEWS ≤ 2) and/or mechanical ventilation

Refer the Appendix 3 for NEWS score.

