9.5.2. Analysis of efficacy variables

9.5.2.1. Primary analyses

The proportion of subjects with undetectable SARS-CoV-2 at PCR at day 7 after randomization (virologic endpoint) and the proportion of subjects who not requires supplemental oxygen therapy (NEWS ≤ 2) and/or mechanical ventilation at day 14 after randomization (clinical endpoint) will be separately analyzed by means of logistic regression models adjusting by pre-defined factors as center, age, gender and post-menopausal status. Additional covariates may be defined in the SAP. Each treatment arm will be compared independently with the placebo.

The null hypothesis for the virologic endpoint is that proportion of treated subjects with undetectable SARS-CoV-2 at PCR at day 7 after randomization is lower or equal the placebo one ($\pi_{PLACEBO}$). Two sets of null and alternative hypotheses are provided, one for each treatment dosage:

$$H_{01-60mg}: \pi_{RALOXIFENE-60mg} \leq \pi_{PLACEBO}$$

$$H_{01-120mg}: \pi_{RALOXIFENE-120mg} \leq \pi_{PLACEBO}$$

$$H_{11-60mg}: \pi_{RALOXIFENE-60mg} > \pi_{PLACEBO}$$

$$H_{11-120mg}: \pi_{RALOXIFENE-120mg} > \pi_{PLACEBO}$$

The null hypothesis for the clinical endpoint is that proportion of treated subjects who not requires supplemental oxygen therapy (NEWS ≤ 2) and/or mechanical ventilation at day 14 after randomization is lower or equal the placebo one ($\pi_{PLACEBO}$). Two sets of null and alternative hypotheses are provided, one for each treatment dosage:

$H_{02-60mg}: T_{RALOXIFENE-60mg} \leq \pi_{PLACEBO}$ $H_{02-120mg}: T_{RALOXIFENE-120mg} \leq \pi_{PLACEBO}$ $H_{12-60mg}: T_{RALOXIFENE-60mg} > \pi_{PLACEBO}$ $H_{12-120mg}: T_{RALOXIFENE-120mg} > \pi_{PLACEBO}$

Superiority of raloxifene will be claimed if at least one null hypothesis is rejected, at interim or at final analysis according to criteria shown in section 9.3.

Sensitivity analyses will be defined in the SAP to assess the robustness of results on primary endpoints versus the presence of missing data (unexpected) and the presence of protocol deviations.

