8 STATISTICAL METHODOLOGY AND CONSIDERATIONS

8.1 ADJUSTMENTS FOR COVARIATES AND FACTORS TO BE INCLUDED IN ANALYSES

In the analysis of primary endpoints and secondary endpoints, the following factors/covariates will be considered in the Binary Logistic regression and Repeated Measures Logistic regression model as described in the SAP section 14.1

- Treatment group;
- Center;
- Age group;
- Status (Male, Female pre-menopausal status, Female post-menopausal status);
- For Clinical outcome: Baseline NEWS value.

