14.1.2 SECONDARY EFFICACY ENDPOINTS AND ANALYSES

1. Proportion of patients with undetectable SARS-CoV-2 at PCR at day 14 after randomization at day 28 after randomization. Analyses will be performed on FAS population. This endpoint will be derived as below

- Based on Approved molecular test (PCR) result, the responses will be considered as “detectable” if PCR result is “Positive” otherwise “undetectable” if PCR result is “Negative” (Missing PCR result will be considered as missing).

The response (detectable / undetectable) at day 14 and day 28 will be analysed using repeated measures logistic regression model with treatment group, visit and pre-defined baseline factors (center, age and status). Odds ratio will be computed for comparisons of each active treatment group versus placebo at each assessment day i.e., raloxifene (60 mg) versus placebo; and raloxifene (120 mg) versus placebo. Analyses will be performed on FAS population using observed data only.

2. Proportion of patients who does not require supplemental oxygen therapy (NEWS ≤ 2) and mechanical ventilation at day 7 and 28 after randomization. This endpoint will be derived as below

- If collected NEWS score > 2 or mechanical ventilation with result “Yes” then the response will be considered as “Required”. If collected NEWS score ≤ 2 and mechanical ventilation with result “No” then the response will be considered as “Not Required” (if both NEWS score and mechanical ventilation are missing, patient will be considered as missing).

The response (Required / Not Required) at day 7 and day 28 will be analysed using repeated measures logistic regression model with treatment group, visit and pre-defined baseline factors (center, age, status and baseline NEWS). Odds ratio will be computed for comparisons of each active treatment group versus placebo at each assessment day. i.e., raloxifene (60 mg) versus placebo; and raloxifene (120 mg) versus placebo. Analyses will be performed on FAS population using observed data only.

For the above two secondary endpoints, Repeated Measures Logistic regression will be performed using PROC GENMOD in SAS® on the observed data only to estimate difference in proportions between each active treatment versus placebo and its corresponding 95% (2-sided) confidence intervals. Exponential transformation will be used to obtain the odds ratio and corresponding 95% confidence interval. P-values will be reported based on the Wald tests from Type III analyses.

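### SAP 14.1.1 puts treatment-by-covariate interactions into both primary logistic models; the protocol and SAP Table 3 list main effects only, the change is undeclared, and the fallback for non-convergence lets outcome data choose the adjustment set

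*SAP*

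**What the plan says.** SAP 14.1.1 specifies the virologic model as treatment group plus "center, age, status and their interaction effects with treatment group", and the clinical model as treatment group plus "center, age, status, baseline NEWS and their interaction effects with treatment group". It promises one odds ratio per dose against placebo, with Wald tests from Type III analyses in PROC GENMOD. SAP 8.3 applies the same procedure to the per-protocol population.

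Other places describe the same analyses differently:

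- Protocol 9.5.2.1 plans "logistic regression models adjusting by pre-defined factors as center, age, gender and post-menopausal status". It adds that "Additional covariates may be defined in the SAP" and does not mention interactions.
- SAP 14.1, Table 3, gives "Treatment, center, age and status" in both virologic rows and "Treatment, center, age, status and baseline NEWS" in both clinical rows.
- SAP 14.1.2 models the virologic outcome at the secondary visits with "treatment group, visit and pre-defined baseline factors (center, age and status"), and the clinical outcome with the same list plus baseline NEWS.
- SAP 8.1 lists no interactions either, but it refers to the "Repeated Measures Logistic regression model as described in the SAP section 14.1", so it defers to the section in dispute.

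SAP 8.5 has its own interaction screen for subgroups at the 0.15 level. SAP 18 declares four changes from the protocol, and none concerns interactions. SAP 8.2 states that site and gender, the randomisation strata, are both in the primary model.

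If the primary model does not converge, SAP 14.1.1 prescribes GENMOD with an EXACT statement, then one-by-one removal of terms by statistical significance, then an unadjusted Fisher's exact test.

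**The concern.** One rejection among the four primary hypotheses is enough for a superiority claim, so the model behind each test should be settled before unblinding. Here a programmer working from Table 3 and one working from the text of 14.1.1 would fit different models.

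The interaction version has two further problems. The dose effect is no longer a single number, because it depends on the covariate levels or weights at which it is evaluated, and the SAP states neither. The model is also very large for the 68 patients reported in SAP 4.3, so the fallback becomes the likely route to the reported result. That fallback does not say whether a separated fit counts as non-converged. Its removal step uses outcome data to choose the covariates, and it could drop the strata that 8.2 says are included.

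**Working it through.** **1. Text.** Side by side, interactions appear in the two model descriptions of 14.1.1, which 8.3 carries into the per-protocol analysis. They are absent from protocol 9.5.2.1, the four Table 3 rows and the two secondary models. The protocol's permission to add covariates covers baseline NEWS; it does not mention interactions.

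**2. What the odds ratio means.** With interactions, the log odds ratio of dose d for a patient with covariates x is b_d + Σ_k g_dk·x_k. With main effects every g_dk is zero and the value is b_d for everyone, whatever the covariate coding. With interactions, b_d is the effect at the reference levels or at an average, depending on coding. Naming Type III Wald tests does not say at which covariate levels or weights the odds ratio is to be reported.

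**3. Parameter counts.** Let c be the number of centres (not stated; 2 to 8 assumed). Main effects, virologic: 1 intercept + 2 treatment + (c−1) centre + 1 age + 2 status = c+5. The clinical model adds 1 for NEWS, giving c+6. With every factor crossed with three arms, the counts are 3(c+3) and 3(c+4).

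| c | Virologic, main | Virologic, interactions | Clinical, main | Clinical, interactions |
|---|---|---|---|---|
| 2 | 7 | 15 | 8 | 18 |
| 3 | 8 | 18 | 9 | 21 |
| 5 | 10 | 24 | 11 | 27 |
| 8 | 13 | 33 | 14 | 36 |

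Patients per parameter with interactions: 68/15 = 4.5 down to 68/33 = 2.1 (virologic), and 68/18 = 3.8 down to 68/36 = 1.9 (clinical).

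**4. Separation.** Simulated trials of 68 patients were checked for complete or quasi-complete separation by linear programming. From the documents: 1:1:1 allocation, 25% vs 50% (virologic) and 50% vs 75% (clinical). Assumed: status 50/15/35% (male, pre-menopausal, post-menopausal), baseline NEWS 0/1/2 at 40/35/25%, no covariate effects, no missing outcomes. With equal centres and 1,500 replicates:

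| c | Virologic, interactions | Virologic, main | Clinical, interactions | Clinical, main |
|---|---|---|---|---|
| 2 | 80.1% | 1.4% | 88.0% | 3.1% |
| 3 | 84.1% | 1.0% | 92.9% | 4.1% |
| 5 | 98.6% | 1.7% | 99.6% | 5.1% |
| 8 | 100% | 8.5% | 100% | 23.1% |

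Equal centres flatter the main-effects model. When centre sizes vary at random (300 replicates per setting, 2–8 centres), main-effects fits separate in 0–23% (virologic) and 2–41% (clinical) of trials, while interaction fits still separate in 79–100% and 88–100%.

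**5. Sensitivity.** With status in equal thirds and only two centres, interaction-model separation falls to 51–53% (virologic) and 64–78% (clinical); with five or more centres it remains 99–100%. If few patients need support, the main-effects clinical model also struggles: 37–96% separated at an assumed 80% vs 90% (2–8 centres), and 83–100% at 90% vs 95% (3–8 centres).

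**6. Power, for illustration.** The per-comparison level is 0.025/4 = 0.00625 one-sided; solving the two-look Pocock equation at that level returns the protocol's boundary of 2.69640. A plain two-proportion test at 0.00625 with 22–23 per arm has 21–22% power per comparison, before any modelling question arises. Simulated power for either dose is 28–34% with main effects, 23–24% with Fisher's test, and at most 2.3% for the interaction model before any fallback. If the removal step is reached it is 20–29% in most settings, and 12–15% with two centres and reference coding. A virologic null run of that step (25% in all arms, 1,800 replicates, 3 and 5 centres) rejected for either dose in 0.1–0.4% of trials.

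**The case against.** The best defence is that there is one operative specification. Section 14.1.1 is the only place that states the primary model in full. Table 3 is a summary whose factor column need not show interactions, 8.1 defers to 14.1, the secondary models concern other visits, and protocol 9.5.8 leaves technical detail to the SAP. Much of this is fair, and 8.1 should carry little weight. It does not remove the problem. Read that way, 14.1.1 is an undeclared departure from the protocol, and at 68 patients it is a model that usually separates.

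It is also true that the fallback has a fixed order and a definite last step. A reader might infer that the primary analysis is wholly open; the documents do not support that. What is open is the trigger, the terms to which the EXACT step applies, and which terms survive removal.

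A reader might infer that the interactions were added after seeing results. The documents do not show this: SAP 4.4 places authorisation of the SAP, database lock and unblinding ahead of the final analysis.

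The percentages rest on assumed centre numbers and covariate mixes, and that criticism stands. The textual conflict and the formulas for the parameter counts do not depend on those mixes. One further gap stands: 8.1 lists age group where 14.1 lists age. If age group is the median split of 8.5, either form takes one parameter, so the counts hold, but the form should be stated.

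**Conclusion.** The point holds and should be resolved before unblinding. The plan gives two descriptions of the primary model for both endpoints. The one in 14.1.1 is undeclared, leaves the reported odds ratio undefined, and separates in about 80–100% (virologic) and 88–100% (clinical) of simulated trials at the planned rates, under the assumed 2–8 centres and covariate mix. The fallback then decides the reported analysis, with a removal step driven by outcome data.

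Three stronger readings are tempting and not supported. First, inflated type I error: the one null run showed none, although it covered only the virologic endpoint with 3 and 5 centres. Second, that the interactions explain the lack of power: most of the shortfall from 80% comes from stopping at 68 patients, and the power figures are illustrative only. Third, that deleting the interactions settles the model: main-effects fits still separate in about 0–23% and 2–41% of trials, and far more often if few patients need support.

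**What to change.** Before unblinding:

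1. In 14.1.1, delete the interaction phrase from both model descriptions, so that they match protocol 9.5.2.1, Table 3 and the secondary models. Keep interactions in the 8.5 screen. State at the same time whether age enters as a group or as a continuous variable.
2. State that complete or quasi-complete separation counts as non-convergence.
3. Replace removal by significance with a simplification order fixed in advance that does not use outcome data. One example is pooling small centres by a stated rule and reducing status to gender, with Fisher's exact test last. The exact order is the sponsor's choice. As a guide, of 1,117 separated main-effects fits simulated at the planned rates, dropping NEWS and age first cured none, then reducing status to gender cured 305, pooling all centres cured 780, and 32 went to Fisher's test (305 + 780 + 32 = 1,117).

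The cost is SAP wording and code, with some stratum detail lost in trials where centres are pooled.
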